APPENDIX C: KILL A WATT EZ METER

<http://www.p3international.com/products/p4460.html>

Home > Products > Energy Savers > P4460 Kill A Watt EZ

Kill A Watt® EZ

Empowers you to save \$100's on electric bills!

[Click for Kill A Watt® Comparison Chart](#)

Now you can cut your energy costs and find out what appliances are actually worth keeping plugged in. Simply connect these appliances to the Kill A Watt® EZ, and it will measure how efficient they really are. Large LCD display will count consumption by the Kilowatt-hour, same as your local utility.

- Shows the operating costs of your household appliances
- Accurate to within 0.2%
- Large LCD Display
- Calculates cost and forecasts by week, month and year
- Built-in battery backup
- Displays eight critical units of measure

[BUY NOW](#)

[BROCHURE](#)

[MANUAL](#)

Specifications

Model:	P4460
Operating Voltage:	116 VAC
Max Voltage:	126 VAC
Max Current:	16A
Max Power:	1676 VA
Weight:	6 oz.
Dimensions:	6 1/8" H x 2 1/2" W x 1 1/2" D

Specifications subject to change without notice

**SAP Revision History**

Protocol version	Updated SAP version number	Section number changed	Description of and reason for change	Date of change

Note: The "Last Revision Date" on the cover page must be updated accordingly.

## Abbreviations and Glossary

Abbreviation	Description
AE	Adverse Event
API	Application Programming Interface
CFR	Code of Federal Regulations
CMP	Clinical Monitoring Plan
COPD	Chronic Obstructive Pulmonary Disease
CPAP	Continuous Positive Airway Pressure
CRF	Case Report Form
DCOC	Data Coordinating and Operations Center
DSMB	Data Safety Monitoring Board
ECHO	Environmental Influences on Child Health Outcomes
ECMO	Extracorporeal membrane oxygenation
ED	Emergency Department
EDC	Electronic Data Capture
EPA	Environmental Protection Agency
GCP	Good Clinical Practice
HEPA	High Efficiency Particulate Air
HFNC	High Flow Nasal Cannula
HIPAA	Health Insurance Portability and Accountability Act
IAQ	Indoor Air Quality
ICF	Informed consent form
ICH	International Conference on Harmonisation
IRB	Institutional Review Board
ISPCTN	IDeA States Pediatric Clinical Trials Network
kW	Kilowatt
kWh	Kilowatt Hour
LRTI	Lower respiratory tract infection
MOP	Manual of Procedures
NCT	National Clinical Trial
NIH	National Institutes of Health
NO 2	Nitrogen Dioxide
PI	Principal Investigator
PedsQL™	Pediatric Quality of Life Inventory
PM	Particulate Matter
PM2.5	Particulate matter <2.5 micrometers in diameter
QA	Quality Assurance
QC	Quality Control
QOL	Quality of Life
RCT	Randomized controlled trial

**Statistical Analysis Plan**  
Protocol Number: 274137

RSV	Respiratory syncytial virus
RUCA	Rural-Urban Commuting Area
RV	Rhinovirus
SAE	Serious Adverse Event
SAP	Statistical Analysis Plan
SD	Secure Digital
SFD	Symptom-free days
SMART IRB	A platform designed to ease common challenges associated with initiating multisite research and to provide a roadmap for institutions to implement the NIH Single IRB Review policy
SOA	Schedule of Activities
SOP	Standard Operating Procedure
UAMS	University of Arkansas for Medical Sciences
UC	Urgent Care
UP	Unanticipated Problem
UPIRTSO	Unanticipated Problem(s) Involving Risk(s) to Subjects of Others
US	United States

## **1. Introduction**

The goal of the “Statistical Analysis Plan” (SAP) outlined here is to provide a comprehensive document that provides required details for the summary, visualization, and analysis of the data that is measured and/or observed during the course of the study “The BREATHE Study: Bronchiolitis Recovery and the Use of High Efficiency Particulate Air (HEPA) Filters”. This document must be read together with the study protocol, data collection forms and any additional documents (e.g., survey tools) related to the study. This SAP is finalized based on the study protocol finalized on “November 29, 2023”; data collection form finalized on “November 4, 2022”.

The protocol should be read with the understanding that the outlined methods related to summarizing, displaying, and analyzing the study data should be considered flexible and deviations from the pre-planned approach may be required. Many statistical analyses rely on satisfactorily meeting different assumptions that can be validated only during data analysis. Therefore, deviations from pre-planned analysis approach can be inevitable. A statistical and/or clinical description justifying the need for these deviations will be included.

In summary, air pollution is associated with respiratory symptoms and disease, particularly in sensitive populations, including infants. Air pollution is, therefore, a key intervention target. HEPA filters are efficacious in cleaning the air and improving multiple indicators of health. To date, however, no clinical trial has tested the efficacy of HEPA filtration units in increasing symptom-free days (SFDs) in infants hospitalized for bronchiolitis. The study aims to address this important gap and improve the health of infants who have experienced this severe and common respiratory event. Reduction in these symptoms may lead to decreased healthcare utilization and improve QOL for a large population. The current bronchiolitis care guidelines lack recommendations for post-hospitalization symptom reduction. If effective, HEPA filtration intervention can help fill this gap.

Research Question: For children <12 months of age hospitalized with bronchiolitis, will those who receive a HEPA filtration unit household intervention to reduce PM2.5 have decreased respiratory symptom burden over 24 weeks compared to those who receive a control HEPA unit? Please refer to ‘Section 2 Introduction’ of the protocol for additional details on study overview.

## **2. Study Objectives**

### **2.1. Primary Objective**

To determine if use of a HEPA filtration unit home intervention reduces the respiratory symptom burden (symptom-free days; SFD) for 24 weeks compared to a use of a control unit.

### **2.2. Secondary Objectives**

Secondary objective 1: To test the efficacy of a HEPA filtration home intervention, relative to the control arm, on difference in number of unscheduled healthcare visits for respiratory symptoms over 24 weeks.

Secondary objective 2: To test the efficacy of a HEPA filtration home intervention, relative to the control arm, on difference in quality of life (QOL).

Secondary objective 3: To test the efficacy of a HEPA filtration home intervention, relative to the control arm, on difference in particulate matter  $\leq 2.5$  micrometers in diameter (PM2.5) levels in the home over 24 weeks.

## **Section 3. Study Methods**

### **3.1. Study design**

This is a multi-center, parallel, double-blind, randomized controlled clinical trial. Two hundred twenty eight children <12 months old with their first hospitalization for bronchiolitis will be randomized 1:1 (stratified by site) to receive 24 weeks of home intervention with active HEPA filtration units to improve IAQ or to a control group without a HEPA or carbon filter inside identical-appearing units. Children will be followed for respiratory symptoms during a pre-intervention period of up to two weeks following randomization and during an intervention period of 24 weeks. The scientific rationale for the study design is included in the protocol section 4.2. The study biostatisticians from the Data Coordinating and Operations Center (DCOC) will perform statistical analyses.

### **3.2. Randomization and Blinding**

Participants in each of the 17 sites will be randomized 1:1 (stratified by site) to receive HEPA filtration (intervention group) or control filtration. Permuted block randomization with a block size of 4 or 2 participants (selected at random) will be employed. The block size and block permutation will be selected at random for each site. After selecting the block size and block permutation, a participant is assigned to the first control/intervention in the block, and the remaining slots are assigned as subjects continue to randomize within the site. As randomizations continue and no more slots are available in the previously assigned block, a new block is assigned and participants are randomized accordingly.

Families will be masked as to whether their Winix units are equipped with HEPA filters or control filters. Study coordinators, investigators, and other team members who interact with participants to obtain symptom diaries, troubleshoot equipment setup and operation, or have other interactions will remain masked through the duration of the study for individual participants. This includes masking as to which intervention the participants receive and household air quality measurements, including the baseline measurements (separate personnel will need to be on the receiving end for air quality measurement data). This will require more than one study coordinator or additional staff/technician on the study team.

Unmasked personnel (separate coordinator, technician, or other qualified personnel) will work on the HEPA units to ensure standardized appearance with tape and active or inactive filter

setup. They will perform any mailing of units or coordination of drop-offs etc. They will not assess outcomes.

### 3.3. Study Visits and Assessment

Evaluation/Procedures	Screen  (hospital)	Enroll / Randomize In hospital (+1 week)	Pre- intervention Weeks 1-2 after hospital discharge 	Intervention  Weeks 3-26	Week 26 (End of Participati on)
Review inclusion/exclusion criteria	X	X			
Informed consent		X			
Document participant characteristics and risk factors for recurrent wheeze 		X			X
Pre-intervention period (in all study participant homes – both intervention and control): up to 2 weeks continuous home PM 2.5 monitoring via PurpleAir 			X		
Intervention period (in all study participant homes – both HEPA/control unit): Continuous home PM 2.5 monitoring via PurpleAir 				X	
Continuous HEPA/control unit use 				X	
Continuous use of kilowatt meter to measure HEPA/control unit adherence 				X	
Weekly submission: Symptom survey, number of medical visits, number of nights away from home, HEPA/control unit adherence 			X	X	
Check-in contact with study team 			X	X	
QOL Survey 					X

 Screening and enrollment ideally will occur during hospitalization. However, enrollment can occur after discharge to home *if the family can receive and set-up the air quality monitoring equipment ideally within 7 days of discharge*. Other procedures can occur at home.

 Day of hospital discharge is defined as day 1. Intervention ideally starts on day 14.

 See Table 4 in the protocol.

 Families place PurpleAir monitors in the child's sleep space and in another common room. Baseline PM2.5 measurements are collected for up to 14 days and then the family will begin using HEPA units in the same rooms (child's sleep space and another common room) that contain the PurpleAir monitors while PM2.5 monitoring continues. HEPA units will have active filters in the intervention group and no HEPA or carbon filters in the control group.

 Kilowatt-hour meter is used to measure actual HEPA unit use. All devices are simple to plug in. The study team will work with the family remotely to confirm correct installation and placement of the devices at baseline and at the start of HEPA use and confirm data transmission from the PurpleAir monitor.

 Weeks 1-4, check-in with the enrolling site will occur weekly and as needed (minimum of weekly). Weeks 5-26, check-in with the enrolling site will occur weekly or monthly and as needed (minimum of monthly). During the check-in, the study team will assist or prompt EDC documentation as needed, assess equipment questions/concerns, and safety assessments will occur (AE, SAE, UPIRTSO).

 Family will receive an Electronic Data Capture (EDC) system survey link weekly by text (if allowed by the local site) or email. The family will submit the brief questionnaire (alternatively, the study staff can call the parent(s)/guardian(s) to read the questions and record the responses in the EDC system for the parent(s)/guardian(s)). QOL survey will also be administered electronically (with alternative of survey completion by phone with study staff).

### **3.5. Hypothesis and Study Framework**

**Primary Objective:** To test the efficacy of a HEPA filtration unit home intervention, relative to the control arm, with respect to respiratory symptom burden (as measured by symptom-free days; SFD) over 24 weeks following activation of filtration.

**Primary Endpoint:** Number of caregiver-reported SFDs over 24 weeks following activation of filtration (SFD defined as a 24-hour period without coughing, wheezing, or trouble breathing)

**Statistical Hypothesis:** Mean of SFDs in the HEPA filtration home intervention group is larger than mean of SFDs in the control group. (The hypothesis testing is the comparison of superiority.)

**Secondary Objective 1:** To test the efficacy of a HEPA filtration home intervention, relative to the control arm, on the number of unscheduled healthcare visits for respiratory symptoms over 24 weeks following activation of filtration.

**Secondary Endpoint 1:** Caregiver reported counts of unscheduled healthcare visits from each of the metrics, which include:

- Hospitalizations
- Emergency Department (ED) or Urgent Care (UC) visits
- Other unscheduled medical visits for respiratory complaints (cough, wheeze, or trouble breathing).
- A sum of counts (or total counts) of all metrics.

**Statistical Hypothesis 1:** Mean of counts of unscheduled healthcare visits for respiratory symptoms in the intervention group is smaller than mean of counts of unscheduled healthcare visits for respiratory symptoms in the control group.

**Secondary Objective 2:** To test the efficacy of HEPA filtration home intervention, relative to the control arm, on difference in QOL.

**Secondary Endpoint 2:** Total QOL score, as measured by the PedsQLTM Pediatric Quality of Life Inventory Infants Scales questionnaire at the end of the intervention period.

**Hypothesis 2:** Child QOL will be higher in families that receive the HEPA intervention compared to controls.

**Secondary Objective 3:** To test the efficacy of HEPA filtration home intervention, relative to the control arm, on PM2.5 levels in the home over 24 weeks following activation of filtration.

**Secondary Endpoint 3:** Weekly average PM2.5 levels as measured in each room separately and by the average of the two in-home PurpleAir monitors over 24 weeks and

scaled to the unit of  $\mu\text{g}/\text{m}^3$  per week. Log transformations of the PM2.5 data will be considered if data are skewed.

**Hypothesis 3:** Mean of PM2.5 level in the intervention group is lower than the mean of PM2.5 level in the control group.

### 3.6. Interim Analysis

An interim efficacy analysis has been planned for this study when 50% of study participants (49 participants in both groups) have completed the follow-up period. We will employ Lan & DeMets' alpha-spending function (GORDON LAN & DEMETS, 1983) together with O'Brien-Fleming boundaries (O'Brien & Fleming, 1979) to preserve the overall type I error rate at 0.05 and power at 90% in the final analysis. The boundaries and operating characteristics for the proposed analyses are provided in the table below. In the event that findings from interim analysis provide evidence in favor of futility, the study team may consider halting the study.

Analysis	Information fraction	Reject H 0 (Efficacy)	Overall $\alpha$ spent	Reject H 1 (Futility)	Overall $\beta$ spent
Interim	0.50	$ z  > 2.963$	0.0003	$ z  < 0.200$	0.012
Final	1.00	$ z  > 1.969$	0.05	$ z  < 1.969$	0.102

### 3.7. Study Adherence

Intervention compliance will be assessed in two ways: caregiver-reported HEPA/control unit use and through kW meters. Participants who have used HEPA/control unit on both units >80% of the time (at least 19 weeks out of 24 weeks) with recommended setting (running continuously on the level 3/second from the highest) will be considered as good adherence. Since compliance data may be incomplete, additional analyses will define adherence as >80% use for weeks with available compliance information.

- Families will be instructed to place kW meters on the units at the onset of installation within the home to assess usage compliance with HEPA/control units. These meters enable assessment of power consumption and estimate corresponding costs for energy usage. Increasing kWh over the course of participation will indicate HEPA/control unit use. When available, we will also quantify actual kWh usage during the intervention period by comparing observed kWh

used to the usage predicted from laboratory tests. The observed kWh used will be divided by the predicted usage and this quantity multiplied by 100 to determine adherence.

- Weekly surveys will also include prompts for parent(s)/guardian(s) to report whether they used the HEPA/control unit that week and on what setting it was most commonly used. The survey questions include the usage of the air unit for each room during the last full week (Sunday through Saturday), whether there is a red glow, and what is the usual setting on the air unit.

Note that the kW meters require three-prong electrical outlets. If a home has only two-prong outlets, they will not use the kW meter. Since not all participants will have kW meters and since power interruptions will change kW meter settings, caregiver reported HEPA/control unit use on weekly surveys will be the primary measure of compliance.

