9.3 POPULATIONS FOR ANALYSES

Analysis Population:

Intent-to-Treat (ITT) Population: The ITT population will include all participants who are randomized to either HEPA filtration (intervention group) or inactive filter unit (control group) (referred to as two groups in the analysis section).

Per-protocol (PP) Population: The PP population will include all participants who are randomized to either the HEPA filter (intervention group) or inactive filter (control group) and have used HEPA unit on average for both units >80% of the time.

The primary set of analyses for this study will be based on ITT population. A separate analysis will be done with the PP population.

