### **4.2. Per-Protocol Population**

Per-protocol (PP) Population: The PP population will include all participants who are randomized to either the HEPA filter (intervention group) or inactive filter (control group) and have used HEPA/control unit on both units >80% of the time with recommended setting (running continuously on the level 3/second from the highest). Intervention compliance will be assessed primarily by caregiver-reported HEPA/control unit use as well as kW meters as described in section 3.7.

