## **6.6. Efficacy Analysis**

### **6.6.1. Primary Efficacy Analysis**

For the primary efficacy measure, we will test the following null hypothesis:

Null hypothesis: Mean of SFDs in the HEPA filtration home intervention group will not differ from the mean of SFDs in the control group.

vs

[figure not shown]
Alternative hypothesis: Mean of SFDs in the HEPA filtration home intervention group is larger than the mean of SFDs in the control group.

The primary endpoint is the number of caregiver-reported symptom-free days (SFD) over 24 weeks following activation of filtration (SFD is defined as a 24-hour period without coughing, wheezing, or trouble breathing). The SFD is observed through a survey each week. The survey is completed on each Sunday, and the symptom-free days are recorded from Sunday in the last week to Saturday, or the day before the survey date. The total SFDs range from 0 to 168 days (7\*24 weeks) assuming no missing data. Complete case analysis is considered as the primary analysis. For situations of missing surveys, see Handling Missing Data section 6.8.

Figure 2 shows the flowchart of surveys of symptom-free days. If a caregiver replies a "No" to the question "During the last full week (Sunday through Saturday), did your child have any coughing, wheezing, or trouble breathing?", then the recorded SFDs in this week are seven. On the other hand, if the caregiver reports a "Yes" in the previous question, and answers a "Yes" in any of the following categories "Daytime Cough", "Daytime Wheeze", "Daytime Trouble

Breathing", and "Nighttime Awakening due to Cough" for all seven days in a week, then the SFD of the survey week will be zero.

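### The 19-of-24-week adherence cut-off in SAP 3.7 is 79.2%, which fails the >80% per-protocol criterion it is meant to express

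*SAP*

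**What the plan says.** SAP 3.7 (Study Adherence) defines good adherence as use "on both units >80% of the time (at least 19 weeks out of 24 weeks"), with the units at the recommended setting. It adds that "caregiver reported HEPA/control unit use on weekly surveys will be the primary measure of compliance", so on the primary measure adherence is counted in whole weeks. Because reports may be incomplete, it also plans a second version: "additional analyses will define adherence as >80% use for weeks with available compliance information".

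SAP 4.2 (Per-Protocol Population) takes families who "have used HEPA/control unit on both units >80% of the time with recommended setting". It gives no week count and says compliance is judged mainly by "caregiver-reported HEPA/control unit use as well as kW meters as described in section 3.7".

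Protocol 9.3 (Populations for Analyses) describes the per-protocol population as those who "have used HEPA unit on average for both units >80% of the time", also without a week count.

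The 19 in SAP 3.7 is the only week count for adherence in either document.

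**The concern.** A minimum number of weeks attached to a percentage should be the smallest count that satisfies the percentage. Nineteen of 24 does not. A programmer who codes the week count and one who codes the percentage will build different per-protocol populations from the same SAP.

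The rule also conflicts with the second version in the same section. A family with all 24 weeks reported and exactly 19 of them adherent is adherent under the main rule and non-adherent under the additional one, on identical and complete data. The additional version exists to deal with missing reports, so the two should agree when nothing is missing.

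At stake is who enters the separate per-protocol analysis. SAP 3.9 states that no blinded data review is planned, so the SAP schedules no blinded step at which the conflict would be noticed and settled. If it surfaces only during analysis, the choice could be made with results by arm in view.

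**Working it through.** **Inputs**

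- Criterion: strictly more than 80% (SAP 3.7, SAP 4.2, protocol 9.3).
- Denominator: 24 intervention weeks (SAP 3.7), which is 7 × 24 = 168 days (SAP 6.6.1).
- Unit of measurement: whole weeks, from the weekly caregiver survey (SAP 3.7).
- Stated cut-off: at least 19 weeks (SAP 3.7).

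**Can the stated 19 be reproduced?** The cut-off is the smallest whole number w with w / 24 > 0.80, that is, w > 0.80 × 24 = 19.2. This gives w = 20, not 19.

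| Adherent weeks | Share of 24 | More than 80%? | At least 80%? |
|---|---|---|---|
| 18 | 75.0% | no | no |
| 19 | 79.2% | no | no |
| 20 | 83.3% | yes | yes |
| 21 | 87.5% | yes | yes |

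**Readings that might rescue it**

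- Reading the criterion as 80% or more instead of more than 80%: the cut-off is still 20.
- Counting days: 0.80 × 168 = 134.4 days, while 19 weeks is 19 × 7 = 133 days, again 79.2%.
- A 23-week denominator: 19 / 23 = 82.6%, which would qualify, but the SAP states 24.
- Rounding 19.2 to the nearest whole number, or down: this gives 19 and is the likely origin of the figure. A minimum cannot be rounded below its own threshold, so it does not justify the number.

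**How many families could be affected?** Only those with exactly 19 adherent weeks. The documents report no adherence distribution, so the following is an illustration. It assumes independent weeks with the same adherence probability p for every family:

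P(exactly 19 of 24) = C(24,19) × p^19 × (1 − p)^5, with C(24,19) = 42,504.

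| Assumed p | P(exactly 19 of 24) |
|---|---|
| 0.80 | 0.196 |
| 0.85 | 0.147 |
| 0.90 | 0.057 |

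**The case against.** The arithmetic is not in dispute. The case on the other side concerns weight and remedy.

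- **Reach.** Both documents base the primary set of analyses on the intention-to-treat population, and the per-protocol analysis is separate. Sample size, power, interim boundaries and the primary result are untouched. This stands, and it limits the importance of the point.
- **The illustrative percentages.** Weekly use within a household is probably correlated, since a family that stops tends to stay stopped. The assumed probabilities also lie close to the cut-off, where the share on exactly 19 weeks is large. The model does not separately represent the two units, the setting or missing weeks. This stands: the figures are not forecasts of misclassification.
- **Coarseness of the measure.** A weekly yes does not record the share of the week the unit ran, so a shortfall of 0.8 percentage points is small beside the measurement error. That is fair on impact, but it does not tell a programmer which of two conflicting rules to use.
- **Intent.** The sponsor may have meant 19 weeks, with the percentage as a loose description. The documents do not say which governs. However, the >80% threshold appears four times (twice in SAP 3.7, once in SAP 4.2, once in protocol 9.3) and the 19 once, so the percentage is the better-supported reading.
- **Protocol 9.3.** The protocol averages use over both units and names no setting, while the SAP requires both units at the recommended setting. Correcting the 19 does not remove that difference. This stands as a separate mismatch.

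**Conclusion.** The concern holds. The week count in SAP 3.7 is wrong for the criterion it expresses: 19 of 24 weeks is 79.2%, and more than 80% needs 20 weeks (83.3%). No reading consistent with the stated 24-week denominator makes 19 correct.

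The effect is confined to families with exactly 19 adherent weeks, and to the per-protocol population and any other analysis that uses the good-adherence classification. The share of families involved is unknown. The range of about 6% to 20% rests entirely on the assumption of independent weeks with a common probability between 0.80 and 0.90. The correction should be made because the error sits in the definition of an analysis population, but it does not threaten the primary analysis.

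**What to change.** In SAP 3.7, change the cut-off from 19 to at least 20 of 24 weeks, and repeat that count in SAP 4.2 so that the population definition is complete where it is stated. If the sponsor did intend 19 weeks, the percentage has to change instead, to one that 19/24 = 79.2% satisfies (for example, at least 79%), in SAP 3.7, SAP 4.2 and protocol 9.3. Either way, record the decision in the SAP revision history before anyone sees results by arm.

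The cost is one number in the SAP and a per-protocol population that is slightly smaller if any family has exactly 19 adherent weeks. While the section is open, the difference between averaging over the two units (protocol 9.3) and requiring both at the recommended setting (SAP 3.7 and 4.2) should be reconciled as well.
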